### 1.2 Secondary Objective

- 1.2.1. To assess the conspicuity of each imaging modality to differentiate radiation necrosis from progressive disease.

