## 3.3 NUMBER OF PARTICIPANTS

One hundred (100) patients will be studied. Up to twenty (20) healthy volunteers will be studied for the purposes of MRI sequence optimization.

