## 7 STATISTICAL CONSIDERATIONS

### 7.1 Definitions

7.1.1 Lesion “**treatment response**” will be defined by size and contrast to noise ratio (CNR). Treatment response will be assessed only in patients with treatment prior to enrollment.

7.1.1.1 Size – treatment response in a single lesion will be considered as a decrease in size of 30%. (see section 5.1)

7.1.1.2 CNR—treatment response will be considered as a decrease in T1 post-contrast CNR of at least 20%. (see section 5.2) by standard T1 post-contrast imaging.

7.1.1.3 Lesions that do not meet these criteria for treatment response will be considered treatment failure.

7.1.2 Disease **recurrence** will be determined by surgical pathology (if available) or at least three months of imaging follow-up. Disease recurrence will be assessed only in patients with treatment prior to enrollment. Imaging findings will be considered recurrent disease in a lesion if:

7.1.2.1 The lesion was initially considered to be a treatment responder.

7.1.2.2 The lesion showed a successive increase in the size of 25% from nadir or a single imaging time point increase of 40%. (see section 5.1)

7.1.2.3 Lesions that do not meet these criteria will be considered radiation necrosis.

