## 7.3 Sample Size

The healthy volunteers' data will only be used for fMRI sequence optimization, quality assurance and will not yield data for the study. The optimization scans on healthy volunteers will not affect the statistical results.

Patients will be divided into 5 groups as discussed above. It is assumed that 90% of patients enrolled will represent either brain metastasis or primary brain tumor, approximately half in each category. We also expect approximately half of each group to have received treatment. We thus expect to have approximately 20-25 patients in each of the first four groups (metastasis with and without treatment and primary brain tumor with and without treatment). The other 10% will be in group 5 and are assumed to be non-tumor mimics of malignancy (for example, stroke, demyelinating disease).

For the primary endpoints, the objective is to calculate the contrast-to-noise ratio (CNR) or equivalent parameter for each method for both primary brain tumors and metastases separately by whether the patient has received treatment. For each imaging modality, we will calculate the CNR separately in the largest lesion/metastasis per patient as well as in all study lesions (see 5.1.3). As an example, for CEST, under the assumption of only a single lesion per patient and an expected mean CEST CNR of 14.9 and corresponding standard deviation of 3.0, 20 patients in a group will give a 95% confidence interval between 13.6 and 16.2. [40] Similar calculations apply for the CNR for each of the other imaging modalities.

We may also combine groups for the purpose of analysis. Continuing the above example, with 45 patients in a group, and the same assumed mean and standard deviation, a 95% confidence interval around the CEST CNR will range from 14.0 to 15.8. Again, similar calculations apply for other imaging modalities.

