## 7.4 Analysis Plan

Patients with metastasis are expected to have on average 2-3 detectable brain lesions each. Patients with primary brain tumors are expected to have a single lesion. All analyses will be performed on the largest lesion within patients, and some analyses will be repeated on a per-lesion basis.

The CNR for each imaging method will be determined and reported along with the corresponding 95% confidence interval. In secondary analyses, for the conspicuity endpoints, the T1 sequence by MRI will be considered the gold standard, and we will compare the conspicuity of each of the other methods to that of T1 sequencing by using McNemar's test. This analysis will first be performed in the largest lesion per patient, and then analyses will be repeated using all lesions.

If enough follow-up images are obtained (see section 4.5), we will compare the CNR in lesions that respond to treatment to those that do not by using a Wilcoxon rank-sum test. We will compare the CNR between baseline and follow-up within patient by using a Wilcoxon signed-rank test. Also, for those lesions that initially respond, some will subsequently grow in size after the initial response. Of these, some will be considered radiation necrosis and some progressive disease. The CNR will be compared between lesions with necrosis and those that are progressive disease using a Wilcoxon rank-sum test.

Exploratory aims will be analyzed with descriptive statistics. fMRI paradigms will be summarized by the group mean and standard deviation. Patient satisfaction will be reported on a five-point Likert scale and compared between the 7T scan and the most recent clinical scan by using a Wilcoxon rank-sum test.

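### For necrosis versus progression, section 7.4 plans a rank-sum test but no estimate of how well each method separates the two, which is what objective 1.2.1 is about

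*Combined protocol and SAP*

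**What the plan says.** The protocol has one secondary objective (section 1.2): "To assess the conspicuity of each imaging modality to differentiate radiation necrosis from progressive disease".

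Section 7.1 sets the reference label. Pathology, or at least three months of imaging follow-up, decides recurrence, and then: "Lesions that do not meet these criteria will be considered radiation necrosis". The population is limited: "Disease recurrence will be assessed only in patients with treatment prior to enrollment".

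Section 7.4 uses that label in one analysis: "The CNR will be compared between lesions with necrosis and those that are progressive disease using a Wilcoxon rank-sum test". The paragraph containing it opens with a condition that enough follow-up images are obtained. It describes the lesions concerned as initial responders that later grow.

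Two other analyses in 7.4 might seem to bear on the objective:

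- An interval estimate: "The CNR for each imaging method will be determined and reported along with the corresponding 95% confidence interval". This is for each method's CNR and is not stated to be by necrosis or progression status.
- A comparison between methods: "we will compare the conspicuity of each of the other methods to that of T1 sequencing by using McNemar's test". This concerns conspicuity relative to T1 and does not use the label either.

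Section 7 mentions no AUC, sensitivity, specificity, cut-off, location shift or interval for the necrosis-progression contrast.

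**The concern.** A rank-sum p-value mixes the strength of separation with the number of lesions. The objective is about the first, and the p-value alone does not recover it. The same degree of separation can be significant or not depending on how many lesions happen to be labelled. A result that just reaches significance is compatible with almost no useful discrimination and with very good discrimination.

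The labelled set could be small, because it is a subset of the treated patients. If it is, a method with useful discrimination could well give p>0.05 and be read as unable to differentiate. The planned test already contains the missing estimate: the Mann-Whitney U divided by the product of the two class sizes is the AUC. The plan does not commit to reporting it. If a measure is chosen once the data are in, that choice is not prespecified.

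**Working it through.** **1. The plan's own precision figure.** Section 7.3 sizes the study on the CEST CNR, with mean 14.9 and SD 3.0. The formula is mean ± 1.96 × SD/√n.

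- n = 20: 14.9 ± 1.96 × 3.0/√20 = 14.9 ± 1.31, or 13.6 to 16.2.
- n = 45: 14.9 ± 1.96 × 3.0/√45 = 14.9 ± 0.88, or 14.0 to 15.8.

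Both agree with section 7.3. They are the only sizing figures, and neither concerns necrosis versus progression.

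**2. How many lesions could be labelled.** Section 3.3: "One hundred (100) patients will be studied". Section 7.3: "It is assumed that 90% of patients enrolled will represent either brain metastasis or primary brain tumor, approximately half in each category", and about half of each group treated. That gives 100 × 0.90 × 0.5 = 45 treated patients. With one lesion each, about 22 v 23 is the most balanced split possible. Only initial responders that later grow enter the comparison, so the number will be lower by an amount the documents do not give. The class sizes and AUCs below are assumptions.

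**3. One AUC, different p-values.** By the normal approximation without ties, z = (AUC − 0.5)/√[(n1+n2+1)/(12·n1·n2)]. At an observed AUC of 0.75:

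- 22 v 23: z = 0.25/0.0870 = 2.87, p = 0.004.
- 10 v 10: z = 0.25/0.1323 = 1.89, p = 0.059.
- 5 v 5: z = 0.25/0.1915 = 1.31, p = 0.19.

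Conversely, the AUC that just reaches p = 0.05 is 0.67 at 22 v 23 (Hanley-McNeil 95% interval 0.51 to 0.83). At 10 v 10 it is 0.76 (0.54 to 0.98).

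**4. Power of the planned test at a true AUC of 0.75.** The test is exact, two-sided, at 5%. Power is by simulation from two unit-variance normal distributions separated by √2 × 0.674 = 0.954.

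| Lesions per class | U needed | Observed AUC needed | Power |
|---|---|---|---|
| 8 v 8 | 51 of 64 | 0.80 | 41% |
| 10 v 10 | 77 of 100 | 0.77 | 47% |
| 15 v 15 | 161 of 225 | 0.72 | 68% |
| 22 v 22 | 326 of 484 | 0.67 | 85% |

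**5. The interval needs a small-sample form.** Hanley-McNeil at AUC 0.75 and 10 v 10 uses q1 = 0.75/1.25 = 0.600 and q2 = 2 × 0.5625/1.75 = 0.643. The variance is (0.1875 + 9 × 0.0375 + 9 × 0.0804)/100 = 0.0125, so SE = 0.112. The plain interval is 0.75 ± 1.96 × 0.112 = 0.53 to 0.97. It excludes 0.5, although the exact p-value at that AUC is 0.063.

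On the logit scale the centre is ln(0.75/0.25) = 1.099 and the SE is 0.112/(0.75 × 0.25) = 0.596. The limits are 1.099 ± 1.168, which transform back to 0.48 and 0.91. That agrees with the exact test.

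In simulation at a true AUC of 0.75, plain DeLong 95% intervals covered about 89% at 8 v 8 and 90% at 10 v 10. DeLong intervals on the logit scale covered about 96-97%.

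**6. Comparing methods on the same lesions.** Take AUCs of 0.85 and 0.70 with a correlation of 0.5 between the estimates, and SE = √(s1² + s2² − 2·r·s1·s2).

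| Lesions | 95% interval for the difference of 0.15 | Power |
|---|---|---|
| 22 v 23 | 0.01 to 0.29 | 56% |
| 15 v 15 | −0.02 to 0.32 | 41% |
| 10 v 10 | −0.06 to 0.36 | 29% |

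**The case against.** **The analysis is secondary and appears conditional.** The study is sized for the precision of CNR, and the paragraph depends on follow-up images being available. This stands. It limits the weight of the point, but 1.2.1 is still the only secondary objective.

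**Naming a test does not forbid reporting an estimate.** This also stands: nothing in 7.4 restricts the output to a p-value. But nothing commits to an estimate either, and the interval that 7.4 does promise is for another quantity.

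**The lesion counts are assumptions.** They are. At 22 v 22 the planned test has about 85% power for an AUC of 0.75, so low power is a possibility and not a finding. The all-lesions analysis could also have more lesions, since 7.4 expects 2-3 per metastasis patient, though lesions within a patient are not independent.

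**Intervals at these sizes can mislead too.** Plain DeLong or Wald intervals would. That is a reason to specify a small-sample form, not to omit an interval.

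**Two stronger readings are not supported.** A reader might infer that 1.2.1 asks which method is best and that the plan fails to answer. The objective speaks of each modality and does not ask for a ranking. Interest in comparison can be inferred only from 7.4 setting the other methods against T1. A reader might also infer that methods will be ranked by p-value, but the documents propose no such thing.

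**Conclusion.** The point holds as a gap between the objective and its analysis. Section 7.4 tests for a CNR difference between necrosis and progression, but plans no estimate of how well any method separates them. No other analysis in the section supplies one.

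Its practical size depends on a count the documents do not give. At a true AUC of 0.75 the planned test would miss significance in about 59% of studies at 8 v 8 (100 − 41), 53% at 10 v 10 (100 − 47), 32% at 15 v 15 (100 − 68) and 15% at 22 v 22 (100 − 85). These figures assume normally distributed values with equal variance, one lesion per patient, balanced classes and a two-sided 5% level, which the documents do not state for this comparison.

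No number in the plan is wrong, and the rank-sum test is a valid test. The documents do not support a claim that the study is bound to be underpowered for this contrast. The remedy is an inexpensive improvement in what is estimated and reported.

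**What to change.** In section 7.4, add the following for the necrosis-progression contrast:

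- For each method, and for T1 post-contrast CNR, report the AUC as U/(n1 × n2) with both class sizes and a 95% interval suited to small samples, for example DeLong on the logit scale. State in advance which class a high AUC refers to, and what is reported if separation is complete, where the logit is undefined.
- When several lesions per patient are used, obtain the interval by resampling patients rather than lesions.
- Report the paired AUC difference between each method and T1 on the same lesions with its 95% interval. Label it descriptive, because it will be imprecise even near 45 patients.
- Keep the rank-sum p-value alongside.

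The cost is a few sentences in the SAP and a few lines of code on data already planned, with no added patients, scans or visits. The drawback is that the intervals will be visibly wide.

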## 1 OBJECTIVES

### 1.1 Primary Objectives

- 1.1.1. To estimate the contrast-to-noise ratio (CNR) for several imaging modalities in brain malignancy as compared with normal brain parenchyma separately by type of malignancy and treatment status. The methods to be studied include Quantitative MRI (T1 and T2 sequencing), Chemical Exchange Saturation Transfer (CEST) MRI, Multiple B-Value Diffusion Imaging (Adv Diff), and Multiple inversion time (TI) arterial spin labeling (ASL) perfusion imaging (Adv ASL).

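### The rank-sum tests of CNR by outcome in 7.4 name no stratification by tumour type; stratifying them would guard cheaply against distortion from tumour-type mix

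*Combined protocol and SAP*

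**What the plan says.** Section 7.4 makes two comparisons of CNR by outcome. If follow-up imaging suffices, "we will compare the CNR in lesions that respond to treatment to those that do not by using a Wilcoxon rank-sum test". For lesions that respond and later grow, "The CNR will be compared between lesions with necrosis and those that are progressive disease using a Wilcoxon rank-sum test". Neither sentence names a stratum, a covariate or a repeat by tumour type.

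The lesions come from both tumour types. Section 7.1 restricts the outcomes to previously treated patients ("Disease recurrence will be assessed only in patients with treatment prior to enrollment", with a parallel sentence for treatment response). Section 7.3 gives the expected mix: "It is assumed that 90% of patients enrolled will represent either brain metastasis or primary brain tumor, approximately half in each category", and "We also expect approximately half of each group to have received treatment".

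Separation by type is written only for the primary estimates. Section 1.1 sets CNR "as compared with normal brain parenchyma separately by type of malignancy and treatment status", and 7.3 repeats that it is calculated "for both primary brain tumors and metastases separately by whether the patient has received treatment". Section 7.3 also allows groups to be combined, with no rule for when or how.

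**The concern.** An unstratified rank-sum test treats all lesions as exchangeable under its null. Its null is therefore that CNR has the same distribution in the two outcome groups, whatever tumour types they contain. The question of interest is narrower: does CNR differ by outcome among lesions of the same type?

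The two questions part company when CNR differs by type and the outcome groups contain different proportions of each type. The pooled test then picks up a difference due to type. If that difference runs with the outcome labels, the test can reject with nothing happening within either type. If it runs against a real outcome effect, the test can miss that effect.

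The necrosis/progression test is the one planned comparison of CNR values that bears on the secondary objective in 1.2. A significant result there could mean only that one group held more metastases. The responder test concerns treatment response, a separate question, but has the same exposure.

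**Working it through.** **The plan's own figures.** Section 7.3 uses a CEST CNR mean of 14.9 and SD of 3.0. The interval is mean ± 1.96 × SD/√n.
- n = 20: 1.96 × 3.0/√20 = 1.31, giving 13.59 to 16.21 (stated 13.6 to 16.2).
- n = 45: 1.96 × 3.0/√45 = 0.88, giving 14.02 to 15.78 (stated 14.0 to 15.8).

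Both reproduce. One mean and SD serve every group; no value is given by tumour type. The plan states no alpha, power or sample size for the rank-sum tests.

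**Number of patients.** 100 × 0.90 = 90 with tumour; 90/2 = 45 of each type; 45/2 = 22.5 treated of each type; about 45 treated in all. With one (largest) lesion per patient, 45 is the ceiling for the responder test. As 7.4 describes it, the necrosis/progression test uses only lesions that respond and then grow, so N = 16 to 20 is taken as an illustrative smaller set.

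**Assumptions not in the documents.** Normal CNR with within-type SD 1 (3.0 units on the CEST example), a gap d between types, outcome shares that differ by type, types equally frequent, two-sided 5% test.

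**Spurious shift, by hand.** With equal numbers of each type and shares 30/70, one outcome group is 0.7/(0.7 + 0.3) = 70% one type and the other group 30%. With no within-type difference, mean CNR differs between outcome groups by (0.70 − 0.30) × d. For d = 1 SD that is 0.4 SD, or 1.2 CNR units. At 35/65 it is 0.3 SD, at 40/60 0.2 SD, and at 50/50 zero.

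**Simulation.** CNR = N(0,1) + d·type + e·outcome, with outcome drawn at random by type.
- Pooled: z = [W − m(N+1)/2] / √[m(N−m)(N+1)/12], with W the rank sum and m the size of one outcome group.
- Stratified (van Elteren): z = Σ w_s[W_s − m_s(n_s+1)/2] / √Σ w_s² m_s(n_s−m_s)(n_s+1)/12, with w_s = 1/(n_s+1).

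N = 45, type gap 1 SD:

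| Shares by type | False rejection, pooled | False rejection, stratified | Power, true 1 SD effect, opposing gap: pooled | Same, stratified |
|---|---|---|---|---|
| 50/50 | 5% | about 5% | 81% | 87% |
| 40/60 | 9% | about 5% | 60% | 86% |
| 35/65 | 15% | about 5% | 48% | 83% |
| 30/70 | 23% | about 5% | 37% | 79% |

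Over the three unequal rows, pooled false rejection is 6%, 8% and 10% for a 0.5 SD gap, and 13%, 23% and 38% for 1.5 SD.

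**Smaller sets, 1 SD gap.** At N = 16 to 20 pooled false rejection is about 6% to 12% for shares 40/60 to 30/70, against about 5% stratified. Power with an opposing gap is 22% pooled against 41% stratified (N = 20, 35/65), and 21% against 36% (N = 16, 40/60).

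**Fixed mix.** Fixing the group composition (22 against 22) instead of drawing outcomes gives 9.8% at 64% against 36% metastases and 24.5% at 73% against 27%, for a 1 SD gap. With an equal mix the pooled test becomes conservative: 2.7%, with power 82% against 87% stratified.

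**When stratifying costs power.** With no type gap, a true 1 SD effect and shares 30/70, power falls from 88% to 79% at N = 45 and from 52% to 41% at N = 20.

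**The case against.** The strongest reply is that pooling is never stated. Section 7.4 is equally silent on type for the primary CNR estimates, which are nevertheless by type because 1.1 and 7.3 say so, and 7.3 makes combining groups optional. This stands in part: pooling is the plain reading of an unstratified two-sample test, not something the plan declares. By-type tests may have been meant, in which case the text should say so.

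A reader might infer that the plan concedes a CNR difference between types by reporting "separately by type of malignancy and treatment status". It does not. Separate reporting asserts no difference, and 7.3 plans with a single mean and SD. If CNR does not differ by type, pooling keeps its 5% error and is the more powerful test when the mix is uneven.

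It is also tempting to apply the N = 45 figures to the necrosis/progression test. The description in 7.4 does not support that, since it limits the test to lesions that respond and then grow. Section 7.1 can be read more broadly, because it labels as necrosis any lesion that misses the recurrence criteria, so the size of the set is uncertain. At 16 to 20 lesions the inflation is modest and neither test has much power.

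Finally, both tests depend on enough follow-up images, in a study whose primary aim is estimation. That limits the weight of the point but does not remove it.

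**Conclusion.** The point holds as a cheap improvement. The tests are not shown to be wrong as written. False rejection needs two conditions together, a CNR gap between types and unequal outcome shares, and the documents give neither. Loss of power needs only the gap.

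Under an assumed 1 SD gap and shares of 40/60 to 30/70, pooled false rejection is about 9% to 23% at the 45-patient ceiling of the responder test. It is about 6% to 12% at the 16 to 20 lesions that are closer to the necrosis/progression subset. Stratified, it is about 5% in both. With equal shares there is no inflation.

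Three wider inferences are not supported:
- The distortion need not be the same for every imaging method, since a type gap may exist for one and not another.
- The two tests do not both serve the secondary objective; only the necrosis/progression test does.
- Treatment status is not a second source of mixing, because 7.1 confines both outcomes to treated patients.

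**What to change.** In 7.4, state that both outcome comparisons use a rank-sum test stratified by tumour type (van Elteren; metastasis against primary brain tumour). Show the CNR difference within each type beside the stratified result, and report the unstratified test as a sensitivity analysis.

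The cost is a sentence or two of wording. The groups in 7.3 already require tumour type for treated patients, so no new data, patients or readings are needed. There are two downsides. Power falls if CNR does not differ by type and the mix is uneven, by the amounts shown in the check above. A type whose evaluable lesions all share one outcome contributes nothing to the stratified test, which is a real possibility in a small necrosis/progression set. The by-type display and the unstratified sensitivity result let the reader see when either applies.

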### 1.3 Exploratory Objectives

- 1.3.1 To assess patient experience in the 7T MRI system compared to their most recent MRI examination.
- 1.3.2 Functional MRI (fMRI) - To assess the typical significance values seen for areas of maximal brain activity associated with each fMRI test.
- 1.3.3 To assess the geometric distortion of a radiation planning sequence on a ultra-high field (UHF) system.

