## 4.5 Patient experience survey

Patients will be given a one-page survey regarding their experience in the 7T MRI system following their scan. For subjects' age 13-17 years old, Research study staff will review questionnaires for completeness and ask subjects with the presence of subject's parent or LAR to complete any missing responses.

4.5.1 [Appendix A]

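### Section 7.4 names an independent-samples rank-sum test for two scans of the same patient, and names no method for several lesions per patient in the all-lesion analyses

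*Combined protocol and SAP*

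**What the plan says.** **Satisfaction.** Exploratory objective 1.3.1 reads "To assess patient experience in the 7T MRI system compared to their most recent MRI examination". Section 4.5 describes one survey: "Patients will be given a one-page survey regarding their experience in the 7T MRI system following their scan". Section 7.4 puts satisfaction on a five-point scale, to be "compared between the 7T scan and the most recent clinical scan by using a Wilcoxon rank-sum test". The preceding paragraph of Section 7.4 handles another within-patient comparison differently: "We will compare the CNR between baseline and follow-up within patient by using a Wilcoxon signed-rank test".

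**Lesions.** Section 7.4 states: "All analyses will be performed on the largest lesion within patients, and some analyses will be repeated on a per-lesion basis". For the primary endpoints, Section 7.3 says "we will calculate the CNR separately in the largest lesion/metastasis per patient as well as in all study lesions", and Section 7.4 attaches a 95% confidence interval to each method's CNR. On the McNemar comparison of conspicuity with T1, Section 7.4 adds: "This analysis will first be performed in the largest lesion per patient, and then analyses will be repeated using all lesions". Section 5.1.3 caps the count at the five largest lesions. Section 7.4 expects an average of 2 to 3 lesions in metastasis patients and one in primary tumor patients. The only interval calculation, in Section 7.3, is made "under the assumption of only a single lesion per patient". Section 7 names no cluster-adjusted, mixed-model, GEE or bootstrap method.

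**The concern.** These are two separate points, and their errors run in opposite directions.

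1. *Wrong test as written.* Both ratings belong to the same patient. The rank-sum test takes its variance from two unrelated samples and ignores the pairing. With positively correlated scores that variance is too large, so real differences are missed. The plan applies the right distinction one paragraph earlier, so this is an internal inconsistency and not a matter of taste.

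2. *Omission.* Lesions in one patient share that patient's biology, treatment, scan session and coil placement, so their CNRs are likely to be correlated. An ordinary confidence interval and an ordinary McNemar test assume independent units. Applied to pooled lesions, the interval is too narrow in the metastasis groups and overstates what the extra lesions add. McNemar's test may reject too often.

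The two rank-sum CNR comparisons (responders against non-responders, and necrosis against progression) share the second problem only if they are among the analyses repeated per lesion, which Section 7.4 does not list. They are also limited to previously treated patients and depend on enough follow-up images.

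**Working it through.** **The plan's own intervals (Section 7.3).** Inputs: mean 14.9, SD 3.0. Formula: mean ± 1.96 × SD/√n.
- n = 20: 1.96 × 3.0/√20 = 1.315, giving 13.585 to 16.215. The plan states 13.6 to 16.2.
- n = 45: 1.96 × 3.0/√45 = 0.877, giving 14.02 to 15.78. The plan states 14.0 to 15.8.

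Both reproduce. They are correct for one lesion per patient and do not carry over to all lesions.

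**Satisfaction.** For n pairs with common variance σ² and correlation ρ, the mean difference has variance 2σ²(1 − ρ)/n. An independent-samples test uses about 2σ²/n. At ρ = 0.5 the effective cut-off is therefore about 1.96/√0.5 = 2.77, a two-sided error near 0.6% in place of 5%.

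The simulation used correlated normal scores cut at −1.5, −0.5, 0.5 and 1.5 into five categories, 100 pairs, and two-sided 5% tests. Power is for a shift of 0.25 SD. The documents give neither a correlation nor an effect size, so both are assumed.

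| Assumed correlation | 0.1 | 0.3 | 0.5 | 0.7 |
|---|---|---|---|---|
| Type I error, rank-sum | 3.9% | 2.5% | 1.1% | 0.2% |
| Type I error, signed-rank | 4.6% | 5.1% | 4.8% | 4.6% |
| Power, rank-sum | 38% | 36% | 35% | 32% |
| Power, signed-rank | 42% | 49% | 61% | 79% |

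With 70 pairs, power is 26/25/23/18% against 30/37/47/63%. Other cut-points and a 0.3 SD shift (100 pairs, correlation 0.3/0.5/0.7) give 52/51/53% against 64/76/91%. At zero correlation the two tests agree.

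**All-lesion CNR interval.** With m lesions in every patient, the design effect is 1 + (m − 1) × ICC. Take 20 patients, m = 2.5 and ICC 0.5 (assumed):
- Unadjusted half-width: 1.96 × 3.0/√50 = 0.83.
- Design effect: 1 + 1.5 × 0.5 = 1.75.
- Adjusted half-width: 0.83 × √1.75 = 1.10.
- Coverage of the unadjusted interval: 2Φ(1.96/√1.75) − 1 = 86%.

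Lesion counts will vary in practice. Section 7.3 implies about 100 × 0.9/4 = 22.5 patients per group. The simulation used 22 patients, 1 to 5 lesions each with mean 2.5, and SD 3.0. The largest-lesion half-width is 1.96 × 3.0/√22 = 1.25. The unadjusted all-lesion half-width is about 0.80, an apparent gain of 1 − 0.80/1.25 = 36%.

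| Assumed ICC | 0.1 | 0.3 | 0.5 | 0.7 |
|---|---|---|---|---|
| Coverage of unadjusted 95% interval | 92% | 87% | 83% | 78% |
| True half-width (1.96 × SD of the estimate) | 0.87 | 1.03 | 1.13 | 1.27 |
| Real gain, 1 − true/1.25 | 30% | 18% | 10% | about 0 |

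Coverage is 93/89/86/81% with a mean of 2.0 lesions and 93/86/80/74% with 3.0. It is much the same with 45 patients. A cluster-robust t interval with degrees of freedom equal to patients minus one covers 94 to 96% throughout. Its half-widths at mean 2.5 are 0.91/1.06/1.17/1.30.

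**McNemar on all lesions (illustrative).** Assuming 70% of lesions conspicuous in both modalities and a mean of 2.5 lesions, type I error stays near 5% if the patient effect is common to both modalities. If each modality has its own patient effect, it is 7/10/15/19% with 22 patients and 6/9/14/17% with 45, at ICC 0.1/0.3/0.5/0.7.

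**Rank-sum CNR comparisons, only if run per lesion (illustrative).** With 22 treated metastasis patients and half the lesions in each status, type I error is 5% if status is unrelated within patient. It is 7/13/17/21% if status is fully shared within patient.

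**The case against.** On the first point, little rides on the result. Section 7.4 opens that paragraph by describing the exploratory aims as descriptive. No alpha, power target or sample size is attached to the comparison, and the error is conservative. At a correlation of 0.1 the loss is about 4 percentage points of power. The survey form is not reproduced, and Section 4.5 describes a single survey about the 7T scan. If it holds one comparative item, the two-score power figures do not apply. All of this stands as to weight. It does not rescue the test: two scores per patient are paired, and one comparative item does not give two samples.

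On the second point, the plan never says that lesions will be treated as independent. It bases its precision on one lesion per patient, says so, and claims no gain from the extra lesions. That is fair, and it is why the point is an omission. But Section 7.3 places the all-lesion CNR under the primary endpoints, and the McNemar repeat is a commitment. The tools as named assume independent units.

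The sizes deserve caution. Every ICC is assumed. The near-zero gain at ICC 0.7 partly reflects pooling, which gives more weight to patients with many lesions. Equal patient weights gave a half-width of about 1.16, a gain of 1 − 1.16/1.25 = 7%. The comparison also assumes that largest and smaller lesions share one mean and SD. The McNemar figures need a binary definition of conspicuity and a rate that the documents do not give. The per-lesion rank-sum figures describe an analysis that may not be run, and necrosis against progression would involve a smaller subset.

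**Conclusion.** Both parts hold, and Section 7.4 should be corrected before analysis.

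The satisfaction test is wrong as written, on the text alone. The consequence is lost power on an exploratory aim: small at a correlation of 0.1, and roughly 26 points (61% against 35%) at 0.5, given two scores per patient and a 0.25 SD shift. It does not produce false positives.

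The missing method for several lesions per patient is secondary, but it touches the all-lesion version of the primary endpoint in the metastasis groups. If lesions are pooled as independent, nominal 95% intervals would cover about 92% to 78% over the assumed ICC range of 0.1 to 0.7. The mismatch and the omission are certain. The sizes depend on correlations that the documents do not supply, and the McNemar and per-lesion rank-sum figures are illustrations only.

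Not affected: the largest-lesion analyses, the intervals in Section 7.3, and primary tumor patients with a single lesion.

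**What to change.** In Section 7.4:

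1. Replace the rank-sum test for satisfaction with the Wilcoxon signed-rank test on within-patient differences. If the survey has a single comparative item, use a one-sample signed-rank test against the neutral score.
2. State that the patient is the cluster in every all-lesion analysis, and name the methods: a cluster-robust, mixed-model or patient-bootstrap interval for CNR; a clustered McNemar test or GEE with robust standard errors for conspicuity; and a clustered rank-sum test if the lesion-level CNR comparisons are run per lesion.
3. List which analyses are repeated per lesion.

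The cost is one test name and a few sentences, with standard software and no new data. All-lesion intervals will be wider, and with 20 to 25 patients per group the robust standard errors need small-sample degrees of freedom.
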